clinically established PET-CT and CT-MPI protocols with the administration of iodinated contrast media. The goal is to include 30 patients, of which 15 should have significant CAD.

PET-MPI Protocol

Patients with suspected CAD who are referred to a clinical PET-MPI will undergo the standard clinical protocol applied in the Emory Nuclear Medicine department. For technical details, please see the PET protocol form included as additional material in the section F.

CT-MPI and CT-FFR Protocol

Image Acquisition

The CT protocol will consist of a CT-MPI acquisition followed by a coronary CT angiography (CCTA) acquisition for the FFR assessment, and it will be performed on a 3rd generation dual-source scanner (Siemens Force) located in the Emory Tower. The CT-MPI acquisitions will be performed first to avoid interference of contrast agent contamination. Between the CT-MPI acquisition and the CCTA will be an adequate time interval to allow the outflow of contrast agent and for the patient to return to a full rest state. CT-MPI will be performed under stress, using the same stressor agent used in the PET-MPI examination to ensure optimal comparison conditions.

For the CT-MPI, dynamic volume CT myocardial perfusion applying the “dynamic shuttle” mode will be used to rapidly cover the entire cardiac anatomy during infusion of a contrast medium bolus for monitoring bolus passage through the left ventricular myocardium. The “dynamic shuttle” mode consists of an image acquisition during rapid, yet smooth back-and-forth movement of the CT scanner table, so that contrast media bolus passage can be evaluated within the entire left ventricle in a time-resolved fashion. This scan acquisition will be performed during pharmacologically induced stress and during rest conditions. CT-MPI studies will be contrast medium enhanced by 50-70 ml of iodinated contrast agent,

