Quantitative analysis of the PET-MPI and CT-MPI acquisition will be performed on per segment (AHA 17 segment model), per territory, per slice and per patient basis. Not only area specific MBF will be calculated but also global perfusion parameters will be taken into account. For the CT-MPI images, MBF will be calculated with different tracer kinetic models and using different temporal sampling rates in order to find the optimal protocol resulting in the highest diagnostic accuracy and lowest radiation dose possible. CT-FFR analysis as well as anatomical evaluation will be performed on all CCTA acquisitions, on per vessel as well as per patient level. Clinical data of the patients will be recorded, such as clinical risk factors, medication use etc. If the patients receive invasive coronary angiography (with or without invasive FFR measurements) or receive treatment after both PET-MPI and CT-MPI were performed, either medicational or interventional, this will be recorded. Readers will be blinded to the results of examinations.

D.2 Statistical Methods / Sample Size Justification

Statistical analysis and graphs will be performed with Sigma Stat 3.5, SigmaPlot 8.0, and Sample Power 2.0 (SPSS, Chicago, IL.). Disease information and demographic variables, such as age and sex, will be summarized by means of descriptive statistics. Data will be reported as means \pm SD or rates with 95 percent confidence intervals. A difference with P value of 0.05 or less will be considered significant. Sensitivity, specificity, accuracy, negative predictive value and positive predictive value will be estimated by using generalized estimating equations, assuming that all measurements in each individual vessel and for each person will be correlated interchangeably. Accuracy of CT-MPI compared with PET-MPI for

detection and grading (in percent of the myocardial slice or myocardial infarct) of perfusion deficit and reduction in myocardial function will be compared. P values for comparisons of reader specific values will be calculated by means of the McNemar test. Kappa analysis will be used to determine agreement for the detection and grading of myocardial ischemic insult and/or infarction during adenosine-stress. This is a preliminary and pilot study, with a convenience sample of 30 patients, that we deem adequate to demonstrate our hypothesis. The analysis includes patient-based analysis and coronary artery-based analysis.

E. PROTECTION OF HUMAN SUBJECTS

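### D.2 leaves the GEE interval method open: with about 15 diseased patients, the usual form under-covers for per-segment sensitivity and fails at an observed 100%

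*Combined protocol and SAP*

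**What the plan says.** D.2 (Statistical Methods / Sample Size Justification) names the estimation method: "Sensitivity, specificity, accuracy, negative predictive value and positive predictive value will be estimated by using generalized estimating equations". The same sentence sets an exchangeable working correlation, in these words: "assuming that all measurements in each individual vessel and for each person will be correlated interchangeably". On reporting it says: "Data will be reported as means \pm SD or rates with 95 percent confidence intervals". It closes with the units of analysis: "The analysis includes patient-based analysis and coronary artery-based analysis".

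D.1 (Image Analysis) adds further units. The quantitative PET-MPI and CT-MPI analysis "will be performed on per segment (AHA 17 segment model), per territory, per slice and per patient basis".

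D.1 (Research Design) sets the size: "The goal is to include 30 patients, of which 15 should have significant CAD".

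D.2 does not give a link function, a variance estimator, a reference distribution, a small-sample correction, or a rule for an observed proportion of 0% or 100%.

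**The concern.** The robust (sandwich) variance in GEE is justified as the number of patients becomes large. The number of segments or vessels per patient does not help. Sensitivity uses only units that are abnormal on PET, so at most the diseased patients contribute. With about 15 of them, the uncorrected sandwich tends to be too small, and a normal quantile ignores its own sampling error.

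A second weakness is separate from the first. If every abnormal unit is detected, there is no variation left from which to estimate a standard error, and GEE gives no usable interval at any unit of analysis.

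Diagnostic accuracy is a main output of the study (Specific Aim 3 and E.4). Intervals that are too narrow, or that collapse to a point, would make CT-MPI and CT-FFR look better established than 15 diseased patients allow.

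**Working it through.** **Plan figure to reproduce.** None. The 30 patients are a convenience sample, and D.2 gives no expected sensitivity, correlation or precision target.

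**Inputs from the plan.** GEE, exchangeable correlation, 95% intervals, 30 patients with 15 diseased, up to 17 segments.

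**Assumed inputs.** Significant CAD is equated with PET-positive, so K = 15 patients contribute to sensitivity. True sensitivity is 0.80–0.95, within-patient correlation (ICC) is 0.1–0.5, and outcomes are beta-binomial. Abnormal segments per diseased patient are 1–10 (uniform), 1–17 (skewed, mean 4.9) or all 17. For the vessel analysis, 1–3 diseased vessels per patient.

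**Formulas** (intercept-only model; patient i has mᵢ abnormal units, of which yᵢ are detected; ρ is the estimated correlation):
- wᵢ = 1/[1 + (mᵢ − 1)ρ]; p̂ = Σwᵢyᵢ / Σwᵢmᵢ
- V = Σwᵢ²(yᵢ − mᵢp̂)² / (Σwᵢmᵢ)²
- raw scale: p̂ ± 1.96√V; logit scale: logit p̂ ± 1.96√V/[p̂(1 − p̂)]
- Mancl-DeRouen: divide each patient's residual by 1 − hᵢ, where hᵢ = wᵢmᵢ/Σwⱼmⱼ, and replace 1.96 by the t quantile on K − 1 = 14 degrees of freedom.

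**Step 1: per-segment sensitivity.** The table gives coverage of the uncorrected interval with 20,000 replicates per row. Samples with 100% observed count as misses.

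| Segments | Sensitivity | ICC | Chance of 100% | Logit | Raw |
|---|---|---|---|---|---|
| 1–10 | 0.90 | 0.1 | 0.2% | 92.0% | 87.0% |
| 1–10 | 0.90 | 0.3 | 1.0% | 88.9% | 82.9% |
| 1–10 | 0.90 | 0.5 | 3.2% | 85.8% | 79.4% |
| 1–17 skewed | 0.80 | 0.1 | 0.0% | 89.9% | 87.5% |
| 1–17 skewed | 0.80 | 0.5 | 0.2% | 90.6% | 85.7% |
| 1–17 skewed | 0.90 | 0.5 | 4.4% | 86.4% | 77.4% |

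Over sensitivity 0.80–0.90 and 1–10 segments, the range is about 85–92% (logit) and 78–90% (raw). A model-based logit variance does not avoid the problem: over all the segment patterns it covers 90–93% at 0.80 and 86–94% at 0.90.

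**Step 2: segment-level specificity.** Normal segments come from all non-diseased patients and from most diseased ones. With 15 patients contributing 17 normal segments and 15 contributing 7–16, logit coverage is 92–94% at specificity 0.80–0.90. The shortfall is 95 − 94 = 1 to 95 − 92 = 3 points.

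**Step 3: the boundary.** If yᵢ = mᵢ for every patient, then p̂ = 1, every residual is 0 and V = 0. The raw-scale interval has zero width. On the logit scale the estimate diverges: a test fit stopped at 26.6 with SE 0.26 and a separation warning, so the interval is effectively 100% to 100%. The chance of this with 15 diseased patients:
- per patient: 0.90¹⁵ = 20.6%; 0.95¹⁵ = 46.3%
- per vessel, sensitivity 0.90: simulated at about 6–13%. As a check, two independent vessels per patient would give 0.90³⁰ = 4.2%, and perfectly correlated vessels 20.6%, so the simulated values lie where they should.

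The exact (Clopper-Pearson) lower limit at 100% is 0.025^(1/n). For n = 15 patients it is 78.2%. If about 83 segments (15 × 5.5) were treated as independent, it would be 95.7%. The fallback must therefore count patients.

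**Step 4: vessel level away from the boundary.** Among samples that have an interval, uncorrected logit coverage is about 95–96%. Counting 100% samples as misses, it is 84–88% at sensitivity 0.90.

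**Step 5: the correction.** Mancl-DeRouen with t(14) on the logit scale covers 93–97% at sensitivity 0.80–0.90. At 0.95 it covers only 76–94%, because it still gives no interval at 100%. Since 78.2% lies below every sensitivity assumed here, the exact fallback turns each of those samples into a covering one. A close relative, an exact interval on the effective sample size throughout, covers 93–99.7% over 0.80–0.95 (90–97% if all 17 segments are abnormal).

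**The case against.** The strongest reply is that D.2 does not commit to the method tested here.

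- A reader might infer that the plan has chosen an uncorrected sandwich with a normal quantile. It has not; the variance is simply not named. The exchangeable working correlation that it does name is not what fails. This stands, so the point is an unspecified method whose usual forms perform poorly at this size.
- A reader might infer that sensitivity per segment by GEE is planned. The GEE sentence names vessel and person, and D.2 ends with patient and coronary artery. The 17-segment wording in D.1 describes quantitative analysis, in which blood flow is calculated. This stands too: the coverage result is conditional on GEE being applied per segment.
- A reader might extend the 15-patient shortfall to specificity and accuracy. The documents do not support that at segment level. Normal segments come from close to 30 patients, and accuracy uses all 30.
- A diverging fit or a zero standard error would be noticed at analysis. True, but without a rule the interval would then be chosen after seeing the result.
- This is a pilot with no precision target or success threshold, so no formal decision depends on these intervals. That limits the consequences. It does not make an interval of 100% to 100% from 15 patients reportable.

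**Conclusion.** The point holds in this conditional form. If the usual uncorrected interval is used per segment, sensitivity is under-covered by about 3–10 points on the logit scale (95 − 92 to 95 − 85) and 5–17 on the raw scale (95 − 90 to 95 − 78). The larger shortfalls occur at sensitivity 0.90 with correlation 0.3–0.5.

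The breakdown at 100% does not depend on the per-segment reading. It is mainly a patient-level and vessel-level problem. Per segment it is uncommon at sensitivity 0.90 (0.2–4% with about 5 abnormal segments per patient).

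The sizes rest on assumed sensitivity, correlation and numbers of abnormal units, none of which the documents give, and on 15 PET-positive patients being reached. Fewer would make both problems worse. Accuracy, PPV and NPV were not simulated. The matter should be settled before analysis, but it does not threaten the study.

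**What to change.** In D.2, state the following:

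1. For clustered estimates (vessel, territory, segment): logit-scale GEE with a bias-corrected sandwich, such as Mancl-DeRouen, and a t reference on the number of contributing patients minus 1.
2. For patient-level estimates: exact Clopper-Pearson intervals.
3. When an observed clustered proportion is 0% or 100%: an exact interval that takes the number of contributing patients as the effective sample size.
4. Which units of analysis will have sensitivity and specificity estimated, so that it is clear whether segments are included.

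The cost is wording plus somewhat wider intervals. With 15 patients contributing equally, hᵢ = 1/15, so the standard error grows by 15/14 and the quantile by 2.145/1.960. Together that is 1.071 × 1.094 = 1.17, or about 17% wider on the logit scale. No change to recruitment or imaging is needed.

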Study Protocol

MyocardiAI CT Perfusion and Coronary Flow: a Comprehensive Cardiac CT Myocardial Perfusion Imaging (MPI)/Fractional Flow Reserve (FFR) and PET-CT MPI Evaluation (The MATCH Investigation)

Protocol Date: May 31, 2023

NCT04316676

[figure not shown]
Emory University

Clinical Study Protocol

MyocardiAl CT Perfusion and Coronary Flow: a CompreHensive Cardiac CT Myocardial Perfusion Imaging (MPI)/Fractional Flow Reserve (FFR) and PET-MPI Evaluation (The MATCH Investigation)

Principal Investigators: [name] [name], PhD; [name]

Origination Date: **10/16/2019**

Emory University
Department of Radiology and Imaging Sciences

CONFIDENTIALITY STATEMENT

This document is the confidential property of Emory University, Radiology Department. No part of it may be transmitted, reproduced, published or used by other persons without the permission of the Principal Investigator.

Emory University

MyocardiAl CT Perfusion and Coronary Flow: a CompreHensive Cardiac CT Myocardial Perfusion Imaging (MPI)/Fractional Flow Reserve (FFR) and PET-CT MPI Evaluation (The **MATCH** Investigation)

TABLE OF CONTENTS

A. SPECIFIC AIMS.....	3
B. BACKGROUND AND SIGNIFICANCE.....	4
C. PRELIMINARY STUDIES.....	7
D. RESEARCH DESIGN AND METHODS (including data analysis).....	8
D.1 Research Design.....	8
D.2 Statistical Methods.....	11
E. PROTECTION OF HUMAN SUBJECTS.....	12
E.1 Risk to the Subjects.....	12
E.1.a Human Subject Involvement and Characteristics.....	12
E.1.b Source of Material.....	15
E.1.c Potential Risks.....	15
E.2 Adequacy of Protection against Risks.....	19
E.2.a Recruitment and Informed Consent.....	19
E.2.b Protection against Risks.....	20
E.3 Potential Benefits of the Proposed Research to the Subjects and Others.....	20
E.4 Importance to the Knowledge to be Gained.....	21
E.5 Subject Safety and Minimizing Risk (Data and Safety Monitoring Plan).....	21
F. ADDITIONAL MATERIAL.....	22
G. REFERENCES AND LITERATURE CITATIONS.....	25

A. SPECIFIC AIMS

The overall goal of this project is to compare the absolute quantification of myocardial perfusion done by using CT myocardial perfusion imaging (CT-MPI) and the coronary flow measured by using CT Fractional Flow Reserve analysis (CT-FFR) to the gold standard represented by PET myocardial perfusion imaging (PET-MPI). The overall goal will be achieved through the following specific aims:

Specific Aim 1: To compare the absolute quantification of myocardial perfusion between CT-MPI and PET-MPI.

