Specific Aim 2: To investigate the correlation between myocardial perfusion measured using CT-MPI and PET-CT MPI, and coronary flow measured using CT-FFR.

Specific Aim 3: To compare the accuracy of PET-CT MPI and combined CT-MPI / CT-FFR approach in the detection of myocardial perfusion abnormalities and coronary stenosis.

B. BACKGROUND AND SIGNIFICANCE

Myocardial perfusion imaging (MPI) is a well-researched technique to evaluate myocardial ischemia. Originally started as a technique limited to nuclear imaging techniques such as Single Photon Emission Computerized Tomography (SPECT) and Positron Emission Tomography (PET), MPI has become available for Computed Tomography (CT) as a result of technological developments. PET-MPI and CT-MPI are the only two techniques that allow for the absolute quantification of myocardial blood flow, directly calculated from the myocardium. Absolute quantification of myocardial perfusion is not only able to quantify lesion specific ischemia but also able to identify global ischemia and microvascular abnormalities, this in contrast to MPI using other modalities (1,2). Some research even implies that subclinical changes, caused for example by diabetes and hypertension, can be detected (2).

The main reason that PET and CT are able to quantify myocardial perfusion is the linear relationship between myocardial blood flow and myocardial tracer/contrast uptake. In figure 3, the relationship between PET and SPECT tracers is shown, where the PET tracers clearly show an superior relationship compared to the SPECT tracers (3). Although both iodine and gadolinium are considered extracellular contrast agents, the advantage of iodine is that the relationship between contrast agent concentration and the change in signal intensity is linear over a wide range and contrast agents concentrations are thus strictly proportional to the signal enhancement, see figure 4 (4). For SPECT tracers as well as gadolinium, used for MRI MPI, the relationship becomes non-linear at higher myocardial blood flows (3,5,6) making absolute quantification impossible.

[figure not shown]

Figure 3. Kinetics of MPI perfusion tracers. Graphical presentation of the relationship between absolute Myocardial Blood Flow (MBF) of the several PET radiotracer and actual tracer uptake.

[figure not shown]

Figure 4. Attenuation density versus iodine concentration. Note the linear relationship even at higher concentrations of iodine (HU: Hounsfield units).

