CT is the latest modality that's being able to perform MPI. Traditionally, this technique was limited by the low temporal resolution and high radiation dose of CT systems, however, on current high-end

systems CT MPI is now possible at equal or even lower radiation doses than the nuclear equivalent. One of the issues with CT MPI is the wide variety of protocols, systems and models used resulting in a wide variety of absolute myocardial blood flow (MBF) values with corresponding ranges of threshold values (7–9). Another issues encountered when comparing CT-MPI to perfusion imaging with other modalities are the significantly lower MBF values measured with CT-MPI (10). Currently, the mathematical models used to calculate MBF, are directly extracted from MRI perfusion studies and an optimal model for CT-MPI has not been determined. Comparing CT-MPI to PET-MPI would help gain insight in the ability of CT to quantify myocardial blood, what the optimal imaging protocol and tracer kinetic model is and is needed to give CT-MPI the last push into clinical implementation on a wide scale.

Another option to evaluate the functional significance of coronary artery disease is measuring the fractional flow reserve (FFR). Fractional flow reserve has been used to measure the functional consequences of specific lesions by measuring a pressure gradient over this lesion, assuming that a drop in pressure will result in an corresponding drop in coronary blood flow and thereby impairing the blood flow to the myocardium (10). This technique has been hampered by the high cost and invasiveness of the procedure. More recently a new approach to calculate FFR has been developed, CT derived FFR (CT-FFR). With the use of computational fluid dynamic and optionally the use of artificial intelligence, it is now possible to calculate FFR from regular CCTA images and anatomically and functionally evaluate the significance of a lesion (11). Several studies have proved the excellent diagnostic accuracy of CT derived CT-FFR with the use of AI, either compared to invasive FFR or in comparison with computation fluid dynamics derived CT-FFR (12–16).

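### Aim 1 compares absolute blood flow between CT and PET, but Section D.2 names only classification statistics and means ± SD, so it specifies no interval for CT-PET bias and no limits of agreement

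*Combined protocol and SAP*

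**What the plan says.** Section A sets the first two aims: "Specific Aim 1: To compare the absolute quantification of myocardial perfusion between CT-MPI and PET-MPI" and "Specific Aim 2: To investigate the correlation between myocardial perfusion measured using CT-MPI and PET-CT MPI, and coronary flow measured using CT-FFR". Section B reports, as a known problem, "significantly lower MBF values measured with CT-MPI" when CT is set against other modalities. It says that comparison with PET "would help gain insight in the ability of CT to quantify myocardial blood, what the optimal imaging protocol and tracer kinetic model is".

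Section D.1 (Image Analysis) plans the measurements at segment, territory, slice and patient level: "Not only area specific MBF will be calculated but also global perfusion parameters will be taken into account". It will calculate CT flow under several tracer kinetic models and temporal sampling rates "to find the optimal protocol resulting in the highest diagnostic accuracy and lowest radiation dose possible".

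Section D.2 is the only statistical section. It names:
- descriptive summaries and a 0.05 significance level;
- GEE with exchangeable correlation for sensitivity, specificity, accuracy and the predictive values;
- an accuracy comparison of CT with PET for "detection and grading (in percent of the myocardial slice or myocardial infarct) of perfusion deficit" and for reduced function;
- McNemar for reader-specific values, a term it does not define;
- kappa: "Kappa analysis will be used to determine agreement for the detection and grading of myocardial ischemic insult and/or infarction during adenosine-stress".

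It closes by saying that there will be patient-based and artery-based analyses, without tying either to a particular test. No section names a paired-difference analysis, limits of agreement, an intraclass or concordance coefficient, a method-comparison regression or a correlation coefficient.

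**The concern.** Aim 1 asks how close CT flow is to PET flow, which is a question about paired continuous values. Every inferential method named in D.2 works on classifications. These can reflect a CT bias, for example under a cut-off shared by both modalities, but they do not estimate it, and the plan states no cut-off rule.

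The selection rule in D.1 does not fill the gap. Choosing a kinetic model on diagnostic accuracy against PET rewards agreement with PET's classification. It does not report agreement with PET's flow values.

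At stake is whether the study can say how far CT flow departs from PET flow in a patient. Several models, sampling rates and unit levels will be computed, so an agreement measure chosen after seeing them leaves room for selective reporting.

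**Working it through.** The plan gives no agreement figure to reproduce. The 30 patients are described as a convenience sample with no formula behind them. From the documents: n = 30, alpha 0.05 (taken as two-sided). Correlations, SDs, flow values, cut-offs, the evaluable number, vessels per patient and within-patient correlations are assumptions.

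**1. Can kappa stand in for agreement in flow?** Assume PET flow has mean 2.2 and SD 0.7 mL/g/min, and CT = 0.6 × PET + noise with SD 0.12.
- Mean bias = −0.4 × 2.2 = −0.88.
- CT mean = 1.32; CT SD = √(0.42² + 0.12²) = 0.437; r = 0.42/0.437 = 0.96.
- With a separate cut-off per modality (PET < 2.0, CT < 1.2), 39% are abnormal on each and kappa = 0.82. A high kappa coexists with a 40% shortfall in flow.
- With one shared cut-off of 2.0, PET calls Φ((2.0 − 2.2)/0.7) = 39% abnormal and CT calls Φ((2.0 − 1.32)/0.437) = 94%. Kappa falls to 0.08 on the same flow data.

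So kappa depends on the cut-off rule and does not measure the bias.

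**2. Can means ± SD stand in?** With PET SD = 1 and CT/PET SD ratio k, the limits of agreement have half-width 1.96 × √(1 + k² − 2kr), in PET SDs.

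| Assumed r | k = 1 | k = 0.6 |
|---|---|---|
| 0.9 | 0.88 | 1.04 |
| 0.7 | 1.52 | 1.41 |
| 0.5 | 1.96 | 1.71 |
| 0.3 | 2.32 | 1.96 |

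The same means and SDs fit every row of a column. They give a point estimate of bias but fix neither its interval nor the limits.

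**3. What would a paired analysis give?** In SDs of the CT-PET differences:
- Bias half-width = t(0.975, n−1)/√n = 2.045/√30 = 0.37.
- Limit half-width = t × √(1/n + 1.96²/(2(n−1))) = 2.045 × √(1/30 + 3.842/58) = 0.65.
- If only 24 are evaluable (assumed): 0.42 and 0.73.

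**4. Is one bias with constant limits enough?** In the scenario of step 1 the SD of the differences is √(0.28² + 0.12²) = 0.305, so constant limits are −0.88 ± 0.60, or −1.48 to −0.28. The mean difference is −0.4 × PET. Mean PET flow in the lowest and highest PET-flow deciles is 2.2 ∓ 1.755 × 0.7 = 0.97 and 3.43, giving −0.39 and −1.37. A single bias would misdescribe patients at both ends.

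**5. Secondary: clustering.**
- *Aim 2 correlation.* At patient level, r = 0.5 with n = 30 has 95% interval tanh(atanh 0.5 ± 1.96/√27) = 0.17 to 0.73. In simulation with 90 vessels (3 per patient), the interval that ignores clustering covers 94.1%, 91.2% and 86.1% at assumed ICC 0.2, 0.4 and 0.6. A leave-one-patient-out jackknife covers 95.1%, 95.6% and 95.0%.
- *McNemar on pooled vessels.* With 3 vessels per patient and within-patient correlation ρ of the paired differences, type I error is about 2(1 − Φ(1.96/√(1 + 2ρ))): 7.4%, 12.1% and 16.6% at ρ = 0.1, 0.3 and 0.5. Simulation gave 7.4%, 12.5% and 16.8%; a cluster-adjusted version gave 4.7% to 4.9%. At patient level, plain McNemar stayed at 4.3% to 4.9%.

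**The case against.** The strongest reply is that this is a declared pilot, the paired flow data will be collected anyway, and nothing is lost if agreement is analysed later. It is true that no data are lost. But the pilot label explains the convenience sample, not the absence of a named analysis for the first aim, and D.2 still sets a significance threshold and calls 30 patients adequate for its hypothesis.

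Four further points limit the claim.
- A reader might infer that D.2 rules out an interval for the bias. It does not. Its sentence on confidence intervals can be read as covering means as well as rates, and it contemplates testing differences. The accurate statement is that a paired interval is not specified. Limits of agreement are absent on any reading.
- A reader might infer that kappa is fixed to a percent-extent scale. That scale stands in the accuracy sentence, and the kappa sentence gives none. Either way, the grading D.2 describes is not a comparison of flow values.
- A reader might infer that the planned McNemar test is invalid. The documents do not say that it is run on vessels, and at patient level it is valid. The inflation in step 5 needs pooled vessels and correlated paired differences. D.2 already clusters the accuracy measures through GEE.
- The missing name of a correlation coefficient for Aim 2, and the undefined reader-specific values, are missing detail rather than wrong methods.

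**Conclusion.** The concern holds for Aim 1 and should be fixed before analysis. The aim is about absolute flow, the background expects CT to be low, and D.2 specifies no estimate of bias with an interval and no limits of agreement. That conclusion comes from reading the sections side by side and depends on no assumed figure.

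The illustrations of size do rest on assumptions. Limits compatible with the planned summaries span ±0.88 to ±2.32 SD at equal SDs, or ±1.04 to ±1.96 PET SD if CT's SD is 0.6 of PET's. The kappa example assumes the stated flow model and cut-offs. The precision figures for a paired analysis need only n = 30 and roughly normal differences.

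The clustering points for Aim 2 and McNemar are secondary and conditional on vessel- or segment-level analysis.

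**What to change.** Add to Section D.2:

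1. **Aim 1.** A paired Bland-Altman analysis of CT minus PET flow, with one lead level stated in advance (for example global stress MBF per patient; the choice is the investigators'). Report the mean bias and both limits of agreement with 95% intervals.
2. **Flow-dependent bias.** Check whether the difference changes with flow level. If it does, use log or ratio limits, or regression-based limits.
3. **Other levels and models.** Give territory- or segment-level results with a patient random effect. Report all results for every kinetic model and sampling rate, beside its diagnostic accuracy.
4. **Secondary, Aim 2.** State the correlation coefficient. Give any vessel- or segment-level correlation an interval clustered by patient, for example a leave-one-patient-out jackknife on the Fisher z scale, using t with patients minus 1 degrees of freedom.
5. **Secondary, McNemar.** Define the reader-specific values and the unit. Use the plain test at patient level only; if it is applied to vessels, use a cluster-adjusted version or a GEE contrast.

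The cost is wording and modest extra analysis, with no new patients, scans or readers. Vessel-level correlation intervals widen: mean widths in the simulation went from 0.312 to 0.339, 0.311 to 0.373 and 0.309 to 0.425 at ICC 0.2, 0.4 and 0.6, or about 9%, 20% and 38%. With 30 patients the limits of agreement will be only moderately precise, and the report should say so.
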